Table 24 - Patients who attended the NTSAD conferences.....	84
Table 25 - Annualized change in 9-HPT in natural history study (NTSAD) from 2015 to 2019	85
Table 26 - Individual listing of 9-HPT in natural history study (NTSAD) from 2015 to 2019	85

LIST OF FIGURES

Figure 1 - Distribution and QQ-plot of Studentized residuals from the linear mixed-effect model on natural history data - With or without log transformation	23
--	----

VERSION HISTORY

This statistical analysis plan (SAP) for Study EFC15299 is based on the protocol amendment 6 dated on 31 July 2023.

A first version of the draft statistical analysis plan was finalized on 17 July 2019 and submitted to the FDA on 26 July 2019, as part of the background package for a Type B meeting (Seq 0015).

The draft SAP was updated on 30 October 2019, following written response received from the FDA on 24 September 2019. The updated version was submitted to the FDA in the initial IND (Seq 0016) on 18 November 2019 as part of the response to Agency written responses.

The draft SAP was amended on 02 March 2021 to include a proposal of interim analysis.

The draft SAP was amended on 25 May 2021 to include FDA recommendation on the proposed interim analysis.

A first version of the full SAP was finalized on 16 November 2022, including recommendation from the EMA and PMDA not to conduct an interim analysis. It also included additional analyses not described in the previous draft versions. This version of the SAP was submitted to FDA and EMA.

The full SAP was amended on 03 August 2023, including changes based on comments and recommendations from FDA, received on 10 March 2023.

The changes in the SAP are detailed in [Table 1](#).

Table 1 - Major changes in statistical analysis plan

SAP version number	Date finalized	Description of statistical changes	Rationale
0.1	17-Jul-2019	Initial version	-
0.2	30-Oct-2019	Addition of code and results of simulations used to investigate the probability of declaring superiority of venglustat under the null hypothesis Clarification of analysis and determination of efficacy of venglustat for the secondary endpoints	As per FDA recommendation As per FDA recommendation
0.3	02-Mar-2021	Addition of interim analysis	Duration and sample size of this study were based on conservative assumptions of stabilization or slight improvement on venglustat. Recent data in PDY13949 study in patients with Gaucher Type 3 disease suggest possible neurological improvement. A similar improvement may also be expected in patients with late-onset GM2 gangliosidosis. An interim analysis may allow early demonstration of efficacy and earlier approval of venglustat in patients with GM2. It would also allow patients enrolled in this study to switch to open label venglustat if efficacy is demonstrated earlier than at the planned final analysis.

SAP version number	Date finalized	Description of statistical changes	Rationale
0.3		
Primary analysis of 9-HPT with Bayesian analysis using non-informative prior is replaced by a Frequentist analysis (Section 3.2.2.2)
 
Clarification and justification that overall Type I error rate is 0.05 one-sided (Section 3.1 and Section 4)
 
Update of prior distribution of placebo slope, used as secondary analysis of the 9-HPT (Section 3.2.2.4.1 and Section 5.7)
 
9-HPT global score not calculated if assessed for only one hand (Section 5.5.1)
 
Update of SAS and results of simulations
	
Bayesian analysis using non-informative prior is equivalent to a Frequentist analysis. Interim analysis is however more easily conducted in a Frequentist framework, using methods developed for group sequential design. Bayesian analysis with informative prior remains a secondary analysis of the 9-HPT.
 
Previous Bayesian analysis had success criterion based on 95% posterior probability. This is equivalent to an alpha level of 0.05 one-sided in a Frequentist framework. An alpha 0.05 one-sided was selected due to the rarity of late-onset GM2 gangliosidosis, the seriousness of this disease and lack of available therapy, as per FDA draft guidance.
 
Prior distribution in the initial SAP was based on data collected from 2015 to 2018 during the National Tay-Sachs And Allied Disease annual conference. Additional data were collected in 2019 and integrated in updated analysis. These data are presented in Section 5.7.
 
9-HPT assessed from only one hand would potentially bias the analysis.
 
Modified SAS code to evaluate the probability of declaring superiority of venglustat with interim analysis and using Frequentist approach. Modified SAS code includes probabilities under different alternative hypotheses as well as under the null hypothesis.

0.4	25-May-2021	Inclusion of analysis of CSF GM2 in the interim analysis	As per FDA recommendation
1.0	16-Nov-2022	
Removal of interim analysis (Section 3.8.1)
 
For primary and secondary endpoints, use of robust ANCOVA in case of outliers (Section 3.2.1.2, Section 3.2.2, Section 3.3.1.2), with pre-specified criteria.
 
Addition of supportive analysis of time to worsening (Section 3.2.2.4.3) and time to improvement of 9-HPT (Section 3.2.2.4.4).
 
Addition of subgroup analysis (Section 3.2.3)
 
Two-step analysis (Section 3.8.2)
 
Description of analysis of exploratory endpoints (Section 3.4), safety (Section 3.6) and other endpoints (Section 3.7)
	
As per EMA and PMDA recommendation
 
Simulations showed that the power of the linear mixed-effect model would be severely impacted if a small proportion of participants have extreme slope (see Section 5.6.3).
 
To provide supportive evidence of the efficacy of venglustat.
 
To explore the consistency of the effect of venglustat in different subgroups.
 
Following addition of an open-label extension period in Protocol amendment 4.
 
Not included in the previous versions, that focused on the analysis of the primary and secondary endpoints.

SAP version number	Date finalized	Description of statistical changes	Rationale
2.0	03-Aug-2023	For primary population, add secondary endpoint of absolute change in CSF GM2 biomarker from baseline to Week 104 (Section 2.1.1 , Section 3.3.1.1 , Section 3.3.1.2.1 , Section 3.3.1.3 , Section 3.3.1.5). For secondary population, add secondary endpoint of acceptability and palatability assessments (Section 1.2 , Section 3.6.1) For primary population, add tertiary/exploratory endpoint of "Additional plasma and CSF biomarkers may include but are not limited to: lipidomics, glycoprotein nonmetastatic protein B (gpNMB), neurofilament" (Section 1.2 , Section 3.7.2) Add descriptive statistics and sensitivity analyses on percent change in CSF GM2 biomarker endpoint with treatment as assigned by randomization (Section 3.2.1.2 , Section 3.2.1.3). For primary population the subgroup analyses will also be conducted on CSF GM2 endpoint (Section 3.2.3 , Section 3.3.1.5). Add 95% confidence interval for supportive and subgroups analyses in addition to 90% confidence interval (Section 3.2.2.4 , Section 3.2.3). The procedure for handling multiplicity of tests for secondary endpoints using a hierarchical approach was replaced by the Hochberg procedure (Section 3.3.1.2 , Section 3.5). Update to endpoint on ophthalmologic in OLE period (Section 1.2 , Section 3.6.3.3). Update the PK analyses (Section 3.7.1)	As per FDA recommendation To align with PIP commitment To clarify the exploratory biomarkers endpoints of primary population according to Amendment 6 of protocol As per FDA recommendation As per FDA recommendation According to Amendment 6 of protocol According to Amendment 6 of protocol add some details about PK sub-study

1 INTRODUCTION

1.1 STUDY DESIGN

This is a multicenter, multinational, randomized, double-blind, placebo-controlled, 2-arm, 104-week study (primary population only) to assess the efficacy and safety of venglustat as compared with placebo in adult participants with a diagnosis of late-onset GM2 gangliosidosis (referred to as the primary population) and venglustat received in an open-label design in participants with a clinical diagnosis of juvenile/adolescent late-onset GM2 gangliosidosis, GM1 gangliosidosis, Saposin C deficiency, Sialidosis Type 1, or juvenile/adult galactosialidosis if any of the sites have such participants meeting the inclusion and none of the exclusion criteria (referred to as secondary population). The secondary population is composed of participants with juvenile/adolescent late-onset GM2 gangliosidosis and ultra-rare conditions within the same biochemical pathway as the primary population. The 104-week treatment period (primary analysis period) will be followed by an open-label extension (OLE) period with venglustat treatment for all patients. The study will be conducted at multiple, multinational sites (approximately 30 sites).

The study will include 4 main periods:

1. Period 1 (screening period from Day -60 to Day -1): Participant and/or participant's parent(s)/legal guardian(s) will sign and date the informed consent and the participant will undergo screening assessments to determine participant eligibility. If all eligibility criteria are met, the participant will start study treatment.
2. Period 2 (primary analysis period, 104-week treatment period): Participants in the primary population will be randomly assigned in a 2:1 ratio to receive venglustat or placebo once daily for 104 weeks in a double-blind manner. Randomization will be stratified on the participant's ability to walk at the baseline visit (yes/no). Participants in the secondary population will receive venglustat for 104 weeks in an open-label manner. Safety, tolerability, pharmacokinetic (PK), pharmacodynamic (PD), and efficacy of venglustat once-daily administration will be determined during the 104-week treatment period.
3. Period 3 (OLE period, 104-week treatment period): Participants in both the primary and secondary population will be automatically entered into the OLE period following completion of primary analysis period (Period 2). All participants will receive venglustat for 104 weeks in an open-label design. Long-term safety, tolerability, PD, and efficacy of venglustat once daily administration will be assessed during the 104-week treatment period.
4. Period 4 (post-treatment safety observation period, 6-week follow-up period). The post-treatment safety observation period will be for 6 weeks after Period 3, and safety and tolerability will continue to be assessed.

After safety data from Week 1/Day 1 to Week 12 visits of the first 5 participants of the primary population are reviewed and considered satisfactory by the data monitoring committee (DMC), enrollment of the secondary population will begin. In addition to the primary population, up to 20 participants in total are planned for the secondary population. An attempt will be made and first prioritized to enroll at least 1 participant (aged 2 years or older) in each of the following disorders: juvenile/adolescent late-onset GM2 gangliosidosis, GM1 gangliosidosis, Saposin C deficiency, Sialidosis Type 1, and juvenile/adult galactosialidosis (secondary population).

1.2 OBJECTIVES AND ENDPOINTS

Table 2 - Objectives and endpoints

Objectives	Endpoints												
Primary													
Primary population:	Co-primary endpoints: 
 To assess the efficacy and pharmacodynamics (PD) of daily oral dosing of venglustat when administered over a 104-week period. 												
Secondary population:	
 Percent change in cerebrospinal fluid (CSF) GM2 biomarker from baseline to Week 104. Annualized rate of change in the 9-hole peg test (9-HPT) from baseline to Week 104. Plasma and CSF GL-1 biomarker and a pathway specific biomarker will be assessed as follows: 												
	
  
 Disease	Biomarker	
   
 GM2 gangliosidosis	GL-1, GM2	
 
 GM1 gangliosidosis	GL-1, GM1	
 
 Sialidosis	GL-1, GM2, GM3	
 
 Galactosialidosis	GL-1, GM1, GM3	
 
 Saposin C Deficiency	GL-1 only	
  
 
 Additional plasma and CSF biomarkers may include but are not limited to: lipidomics, glycoprotein nonmetastatic protein B (gpNMB), neurofilament. 	Disease	Biomarker	GM2 gangliosidosis	GL-1, GM2	GM1 gangliosidosis	GL-1, GM1	Sialidosis	GL-1, GM2, GM3	Galactosialidosis	GL-1, GM1, GM3	Saposin C Deficiency	GL-1 only
Disease	Biomarker												
GM2 gangliosidosis	GL-1, GM2												
GM1 gangliosidosis	GL-1, GM1												
Sialidosis	GL-1, GM2, GM3												
Galactosialidosis	GL-1, GM1, GM3												
Saposin C Deficiency	GL-1 only												
Secondary													
Primary population:	
 To assess the PD of daily oral dosing of and effect of venglustat on selected performance test and scale over a 104-week period. Absolute change in CSF GM2 biomarker from baseline to Week 104. Change in 25-foot walk test (25-FWT) from baseline to Week 104 (in participants able to walk at baseline). Change in the neurological examination of the Friedreich's Ataxia Rating Scale (FARS) from baseline to Week 104. 												
Primary population:	
 To determine the safety and tolerability of venglustat when administered orally once daily over a 104-week period. Changes from baseline to Week 104 in the following: 
 Assessment of adverse events (AEs) and concomitant medication. Physical examination. Neurological examination. Ophthalmological examination. Vital signs. Clinical laboratory evaluations including hematology, biochemistry, urinalysis, and serology. Electrocardiogram (ECG). 												
Primary population:	
 To assess the pharmacokinetics (PK) of venglustat in plasma and CSF. Plasma and CSF venglustat concentrations at prespecified visits over the study duration and plasma PK parameters (when applicable) including maximum plasma concentration observed (C_{max}), t_{max}, and area under the plasma concentration versus time curve calculated using the trapezoidal method over a predefined time period (from time $t = 0$ to 24 hours; AUC_{0-24}). 												

Objectives	Endpoints
Secondary population: 
• To assess the effect of venglustat on selected performance tests and scale over a 104-week period.	
• Annualized rate of change in the 9-HPT from baseline to Week 104.• Change in 25FWT from baseline to Week 104 (in participants able to walk at baseline).• Change in the neurological examination of the FARS (FARS-neuro) from baseline to Week 104.
Secondary population: 
• To determine the safety and tolerability of venglustat when administered once daily over a 104-week period.	
• Changes from baseline to Week 104 in the following:
- Assessment of AEs and concomitant medication- Physical examination.- Neurological examination.- Ophthalmological examination.- Vital signs.- Clinical laboratory evaluations including hematology, biochemistry, urinalysis, and serology.- ECG.
Secondary population: 
• To assess the PK of venglustat in plasma and CSF.	
• Plasma and CSF venglustat concentrations over the study duration and plasma PK parameters (when applicable) including C_{max}, t_{max}, and AUC_{0-24} calculated using the trapezoidal method.
Secondary population: 
• To assess the acceptability and palatability of the venglustat tablet.	
• Acceptability and palatability assessments.

Tertiary/exploratory

Objectives	Endpoints

Objectives	Endpoints

2 ANALYSIS POPULATIONS

The following populations for analyses are defined:

Table 3 - Populations for analyses

Period	Population	Description
Primary analysis	Screened	All participants (and/or participant's parent(s)/legal guardian(s)) who signed the Informed Consent Form (ICF).
	Randomized	All participants from screened population who have been allocated to a randomized intervention by Interactive Response Technology (IRT) regardless of whether the intervention was received or not.
	Population without trial impact (disruption) due to COVID-19	All randomized participants without any critical or major deviation related to COVID-19 and who didn't permanently discontinue treatment due to COVID-19 and who didn't permanently discontinue study due to COVID-19.
	Primary efficacy population	All randomized participants with diagnosis of late-onset GM2 gangliosidosis aged ≥ 18 years. Participants will be analyzed according to the intervention assigned by randomization.
	Primary PD population	All randomized participants with diagnosis of late-onset GM2 gangliosidosis aged ≥ 18 years who received at least 1 dose of study medication and who have baseline and postbaseline assessments of PD. Participants will be analyzed according to the intervention they actually received.
	Primary PK population	All randomized participants with diagnosis of late-onset GM2 gangliosidosis aged ≥ 18 years who received at least 1 dose of study medication and who have at least 1 PK assessment.
	Primary safety population	All randomized participants with diagnosis of late-onset GM2 gangliosidosis aged ≥ 18 years who received at least 1 dose of study medication. Participants will be analyzed according to the intervention they actually received.
	Secondary efficacy population	All enrolled participants with a clinical diagnosis of juvenile/adolescent late-onset GM2 gangliosidosis, GM1 gangliosidosis, Saposin C deficiency, Sialidosis Type 1, or juvenile/adult galactosialidosis.
	Secondary PD population	All enrolled participants with a clinical diagnosis of juvenile/adolescent late-onset GM2 gangliosidosis, GM1 gangliosidosis, Saposin C deficiency, Sialidosis Type 1, or juvenile/adult galactosialidosis, who received at least 1 dose of study medication and who have baseline and postbaseline assessments of PD.
	Secondary PK population	All enrolled participants with a clinical diagnosis of juvenile/adolescent late-onset GM2 gangliosidosis, GM1 gangliosidosis, Saposin C deficiency, Sialidosis Type 1, or juvenile/adult galactosialidosis, who received at least 1 dose of study medication and who have at least one PK assessment.
	Secondary safety population	All enrolled participants with a clinical diagnosis of juvenile/adolescent late-onset GM2 gangliosidosis, GM1 gangliosidosis, Saposin C deficiency, Sialidosis Type 1, or juvenile/adult galactosialidosis, who received at least 1 dose of study medication.
Open-Label extension	Enrolled population	All participants who completed the primary treatment analysis period and accept to continue.
	Efficacy population	All participants from enrolled population.
	Safety population	All participants from enrolled population who received at least one venglustat dose after the 104-week visit.

Participants exposed to study intervention before or without being randomized will not be considered randomized and will not be included in any analysis population. The safety experience of these participants will be reported separately.

Randomized participants for whom it is unclear whether they took the study intervention will be considered as exposed and will be included in the safety population as randomized.

For any participant randomized more than once, only the data associated with the first randomization will be used in any analysis population. The safety experience associated with any later randomization will be reported separately.

For participants receiving more than one study intervention during the study, the intervention group for as-treated analyses will be the one to which the participant was treated with the longest duration.

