5.3 LIFESTYLE CONSIDERATIONS

5.3.1 Meals and dietary restrictions

5.4 SCREEN FAILURES

Screen failures are defined as participants who consent to participate in the clinical study but are not subsequently entered in the study. A minimal set of screen failure information is required to ensure transparent reporting of screen failure participants to meet the Consolidated Standards of Reporting Trials (CONSORT) publishing requirements and to respond to queries from regulatory authorities. Minimal information includes demography, screen failure reasons, eligibility criteria, and any SAE.

A participant cannot be randomized more than once in the study. Participants who fail screening may be rescreened once during the recruitment period in cases where the original screening failure was due to reasons expected to change at rescreening and based upon the Investigator's clinical judgment. Different participant identification will be issued for such participants.

There is no requirement for a waiting period between the screen-failure date and the rescreening date. The interactive response technology (IRT) report will flag rescreened participants. Participants that are rescreened must sign a new consent form. Not all screening assessments are required to be repeated for participants rescreening. Coordination and speech, behavioral, and ataxia assessments are not required to be repeated if performed within the past 3 months. For participants rescreened within 2 weeks of the initial screening visit, the Investigator may use the initial screening visit results for biomarkers, chemistry, hematology, and urinalysis.

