- Any treatment emergent serious adverse events (SAEs).
- TEAE leading to death.
- Any TEAE leading to permanent intervention discontinuation.
- Any treatment emergent AESI.

The AE summaries of [Table 10](#) will be generated with number (%) of participants experiencing at least one event.

Table 10 - Analyses of adverse events

Type of AE	MedDRA levels
All TEAE	Primary SOC, HGLT, HLT and PT
All TEAE by trial impact (disruption) due to COVID-19	Primary SOC and PT
TEAE related to IMP as per Investigator's judgment	Primary SOC and PT
TEAE by maximal intensity	Primary SOC and PT
Treatment emergent SAE	Primary SOC and PT
TEAE leading to permanent intervention discontinuation	Primary SOC and PT
TEAE leading to death (death as an outcome of the AE as reported by the Investigator in the AE page)	Primary SOC and PT
Treatment emergent COVID-19 related AE	Primary SOC and PT
Pretreatment AE	Overview ^a
Pretreatment AESI	Primary SOC and PT
Treatment-emergent AESI	Primary SOC and PT
Post-treatment AE	Overview ^a

a Will include the following AE categories: any AEs, any serious AEs, any AEs leading to death, any AEs leading to permanent intervention discontinuation.

Analysis of deaths

In addition to the analyses of deaths included in [Table 10](#) the number (%) of participants in the following categories will be provided:

- Deaths during the treatment-emergent and post-treatment periods by reason for death.
- Deaths in non-randomized participants or randomized but not exposed participants.

Analysis of adverse events of special interest (AESIs)

Adverse events of special interest (AESIs) and other AEs of interest will be selected for analyses as indicated in [Table 11](#). Number (%) of participants experiencing at least one event will be provided for each event of interest. Tables will be sorted as indicated in [Table 9](#).

Table 11 - Selections for AESIs

AESIs and other AEs of interest	Selection
Pregnancy of a female subject	e-CRF specific tick box on the AE page / specific e-CRF page
Symptomatic overdose (serious or non-serious) with IMP	e-CRF specific tick box on the AE page / specific e-CRF page
Increase in alanine transaminase (ALT)	e-CRF specific tick box on the AE page
New or worsening lenticular opacities and cataracts	e-CRF specific tick box on the AE page

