5.2 APPENDIX 2 PARTICIPANT DISPOSITIONS

The number (%) of participants included in each of the analysis populations listed in [Table 3](#) will be summarized. The reasons for exclusion from the population without trial impact (disruption) due to COVID-19 will be also summarized.

Screen failures are defined as participants who consent to participate in the study but are not subsequently randomized. The number (%) of screen failures and reasons for screen failures will be provided in the screened population.

The number (%) of participants in the following categories will be provided:

- Randomized participants.
- Randomized but not exposed participants.
- Randomized and exposed participants.
- Participants who completed the study treatment period as per protocol.
- Participants who did not complete the study treatment period as per protocol and main reason for permanent intervention discontinuation.
- Participants who completed the study period as per protocol.
- Participants who did not complete the study period as per protocol and main reason for study discontinuation.

The number (%) of exposed and not randomized participants will also be summarized.

In addition, the number (%) of participants screened, screened-failed, randomized, with permanent intervention discontinuation and with early study discontinuation will be provided by country and site.

Protocol deviations

Critical and major protocol deviations (automatic or manual) will be summarized in the randomized population as well as displayed separately according to their relation to COVID-19.

Disposition by visit

Participant disposition by visit will be provided according to trial impact (disruption) due to COVID-19, as reported in CRF.

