5.3 APPENDIX 3 DEMOGRAPHICS AND BASELINE CHARACTERISTICS, PRIOR OR CONCOMITANT MEDICATIONS

The following demographics and baseline characteristics, medical and surgical history and disease characteristics will be summarized using descriptive statistics in the randomized population.

Demographic and baseline characteristics

- Gender (Male, Female).
- Age in years (quantitative and categorical variable: Children (2-11 years), Adolescents (12-17 years), 18 to <65, 65 to <85 and ≥85 years), the two first categories are applicable only to participants in the secondary population.
- Race (White, Black or African American, Asian, American Indian or Alaska Native, Native Hawaiian or other Pacific Island, other).
- Ethnicity (Hispanic, non-Hispanic).
- Weight in kilograms (quantitative and categorical variable: 10 to <15, 15 to <30, 30 to <50, 50 to <100, ≥100).
- Body mass index (BMI) in kg/m² (quantitative and categorical variable: <18.5, 18.5 to <25, 25 to <30, ≥30).

Randomization strata

The randomization strata is only applicable for primary population. The two categories will be presented: able to walk, unable to walk.

Disease characteristics

The time since diagnosis and time since symptom onset will be derived from the subtraction between two years: year of randomization and year of diagnosis or symptom onset. A value of zero means that diagnosis or symptom were occurred the year of randomization.

Based on the same principle, the age at diagnosis and age at symptom onset will be derived from the difference between the year of diagnosis or symptom onset and the year of birth.

Medical or surgical history

Medical (or surgical) history includes previous relevant medical and surgery history collected at baseline. Medical and surgical history will be coded to a LLT, PT, HLT, HLGT, and associated to

a primary SOC using the MedDRA version currently in effect at Sanofi at the time of database lock.

Medical/ surgical history will be summarized in each treatment arm by primary SOC and PT. Events will be sorted by SOC internationally agreed order and decreasing frequency of PT based on the incidence in the primary population.

Alcohol habits at baseline

Alcohol habits include:

- Frequency of alcoholic drinks in the last 12 months (Never/Occasional/At least monthly/At least weekly/At least daily).

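### SAP rules worded by randomization, with no limit to the primary population, misclassify the never-randomized secondary population as screen failures and leave its deviations untabulated

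*SAP*

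**What the plan says.** The schedule of activities in Protocol 1.3 marks randomization as applying to the primary population only. SAP 1.1 has the secondary population receiving open-label venglustat for 104 weeks.

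The rules at issue are these:

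- **Screen failure.** SAP 5.2: "Screen failures are defined as participants who consent to participate in the study but are not subsequently randomized". Protocol 5.4: "Screen failures are defined as participants who consent to participate in the clinical study but are not subsequently entered in the study".
- **Deviations.** SAP 5.2: "Critical and major protocol deviations (automatic or manual) will be summarized in the randomized population", with a separate display by relation to COVID-19. No other set is named.
- **Membership of analysis sets.** SAP 2, below Table 3: "Participants exposed to study intervention before or without being randomized will not be considered randomized and will not be included in any analysis population". The next sentence adds: "The safety experience of these participants will be reported separately". SAP 3.6 gives people who were exposed but not randomized as its example of participants outside the safety population, and SAP 5.2 counts such people on a line of their own.
- **Secondary populations.** SAP Table 3 builds the secondary efficacy, PD, PK and safety sets on enrolment, opening with "All enrolled participants with a clinical diagnosis of juvenile/adolescent late-onset GM2 gangliosidosis".
- **Demographics.** SAP 5.3 covers demographics, history and disease: "disease characteristics will be summarized using descriptive statistics in the randomized population". The same list has child and adolescent age categories that it reserves for the secondary population.
- **Deaths.** SAP 3.6.2 adds a line for "Deaths in non-randomized participants or randomized but not exposed participants".

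**The concern.** A rule that uses randomization to mean being in the trial works for a fully randomized study. Here it does not fit a group whose members are all treated and never randomized. That group has its own primary objective (plasma and CSF biomarkers) and includes all participants under 18.

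Two reported results are at stake. The disposition table could show treated participants as screen failures. The deviation table could leave out an open-label group in which eligibility and conduct need to be visible. In addition, a sentence in SAP 2 is irreconcilable with the table above it, and programmers would have to decide for themselves which one governs.

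**Working it through.** The plan gives no figure on this point, so there is none to reproduce. The check sets the texts side by side and then sizes their literal reach.

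**1. Could secondary participants count as randomized?** Protocol 6.3 has the IRT allocate kits to both populations. SAP Table 3, however, requires allocation to a randomized intervention for membership of the randomized set, and Protocol Table 5 requires a kit allocated through the randomization process. Open-label kit allocation meets neither, so secondary participants are outside the randomized set.

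**2. Screen failures.** A treated secondary participant has consented and has not been randomized, and so is a screen failure under SAP 5.2. The same person has been entered in the study, and so is not one under Protocol 5.4. The SAP has no second definition to set this right. That participant would appear both among the screen failures and in the Table 3 secondary sets, and the disposition counts would not reconcile.

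**3. Deviations.** The only stated set is the randomized population, which holds no secondary participants. The number of secondary-population deviations tabulated under the plan is therefore zero, whatever occurred.

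**4. Exclusion sentence.** Read alone, it reaches every treated secondary participant. Table 3 puts the same people into four analysis sets. Table 4 assigns them endpoints, SAP 3.2.4.2 and 3.3.2.2 plan their analyses, and SAP 3.6 gives them their own safety arm. These instructions cannot all be followed.

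**5. Size.** Inputs: about 57 primary participants (SAP 4) and up to 20 secondary (SAP 1.1).

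- Planned participants: 57 + 20 = 77.
- Literal reach: 20/77 = 26.0% of those planned, which is the whole secondary population and none of the properly randomized primary population.
- Participants already known: Protocol 2.3.1.1 reports 13 participants aged 2 to under 18 enrolled by August 2022. The primary population is adult, so all 13 belong to the secondary population.

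The documents give no number of true screen failures, F. SAP 5.2 takes the percentage over the screened population, so with 77 entered the rate moves from F/(77+F) to (F+20)/(77+F):

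| F (assumed) | Protocol 5.4 definition | SAP 5.2 definition |
|---|---|---|
| 0 | 0/77 = 0% | 20/77 = 26.0% |
| 10 | 10/87 = 11.5% | 30/87 = 34.5% |
| 20 | 20/97 = 20.6% | 40/97 = 41.2% |
| 40 | 40/117 = 34.2% | 60/117 = 51.3% |

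These rows are illustrations on assumed counts, not predictions.

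**6. Same root elsewhere.** SAP 5.3 computes time since diagnosis from the year of randomization and summarizes medications in those randomized and exposed. SAP 5.4 ages children for laboratory abnormality criteria by time since randomization. Secondary participants have no randomization date.

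**The case against.** The strongest reply is that nobody would apply the exclusion sentence to the secondary population. It says that such people will not be considered randomized, which has meaning only for people who were meant to be randomized. The rules after it also deal with anomalies of exposure and randomization: unclear intake, randomization more than once, and receipt of more than one intervention. Table 3, Table 4 and the sections on biomarkers, function, safety, palatability, PK and PD all treat the secondary population explicitly. This stands. A reader might infer from the sentence that the secondary population is dropped; the documents do not support that.

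A reader might also infer that the pediatric safety data disappear. They would not. SAP 3.6 plans a secondary-population safety arm, and even on the literal reading SAP 2 still reports the safety of excluded participants separately.

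Nor does the deaths line lose information. It is additional to Table 10, which already tabulates treatment-emergent events leading to death. At worst, a secondary participant's death is shown in two places.

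On demographics, SAP 5.3 plainly expects secondary participants in its tables: it has age rows for them and says that the randomization strata apply to the primary population only. The named set is loose wording, and no loss follows.

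Disposition is partly covered too, because SAP 5.2 counts participants in every Table 3 population and its completion lines are not restricted to randomized participants.

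None of this reaches the screen-failure definition or the deviations line. For those, the SAP contains no competing text, and evident intent does not tell a programmer which set to use.

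**Conclusion.** The point holds as a minor wording fault with two reporting consequences. Applied as written, SAP 5.2 misclassifies up to 20 treated participants as screen failures, contrary to Protocol 5.4, and provides no tabulation of their critical and major deviations. The exclusion sentence in SAP 2 and the matching example in SAP 3.6 contradict the secondary populations in Table 3. Because the intent to analyze those populations is clear, this is an internal inconsistency and not a loss of data.

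The 26% is the planned share of the secondary population, and it assumes full enrolment of 20 alongside 57. Any shift in the screen-failure rate depends on a failure count that the documents do not give. The co-primary analyses, alpha and power use randomized primary participants only and are unaffected. The secondary-population analyses are descriptive.

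**What to change.** - **SAP 5.2, screen failures:** use the Protocol 5.4 definition, spelled out as consenters who are neither randomized in the primary population nor enrolled in the secondary population.
- **SAP 5.2, deviations, and SAP 5.3, demographics and history:** summarize randomized (primary) and enrolled (secondary) participants separately.
- **SAP 2, exclusion sentence, and the lines on exposed but non-randomized people in SAP 3.6 and 5.2:** limit them to participants intended for the primary population.
- **SAP 5.3 and 5.4, dates counted from randomization:** while making these edits, name a reference date for secondary participants. The first IMP intake, already the Day 1 reference for treated participants in SAP 5.4, would serve.

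The cost is a few phrases in the SAP. No new data are needed, and no confirmatory analysis changes.
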